- Concurrent use of any non-insulin glucose-lowering agent, other than metformin (for example, GLP-1 agonists, Symlin, DPP-4 inhibitors, SGLT-2 inhibitors, sulfonylureas).
- 6. Hemophilia or any other bleeding disorder
- 7. Hemoglobinopathy
- 8. History of heart, liver, lung or kidney disease determined by investigator to interfere with the study
- 9. History of allergic reaction to Humalog or Novolog
- 10. Use of any medications determined by investigator to interfere with study
- 11. Significant chronic kidney disease (which could impact CGM accuracy in investigator's judgment) or hemodialysis
- 12. Concurrent use of any medication that could interfere with the study CGM, such as hydroxyurea
- 13. History of adrenal insufficiency
- 14. History of abnormal TSH consistent with hypothyroidism or hyperthyroidism that is not appropriately treated
- 15. History of gastroparesis
- A condition, which in the opinion of the investigator or designee, would put the participant or study at risk
- 17. Participation in another pharmaceutical or device trial at the time of enrollment or anticipated for during the time period of study participation
- 18. Employed by, or having immediate family members employed by Tandem Diabetes Care, Inc., or having a direct supervisor at place of employment who is also directly involved in conducting the clinical trial (as a study investigator, coordinator, etc.); or having a first-degree relative who is directly involved in conducting the clinical trial

Participant Duration

Approximately 6-12 weeks

Study Endpoints

The adult, pediatric and preschool populations will be combined for the analysis of primary and secondary endpoints. Separate analyses also will be performed for the adult, pediatric and preschool cohorts for the primary and secondary endpoints. CGM data collected during the challenge periods will not contribute to overall analysis of CGM metrics. The three study time periods are the Run-In period with Control-IQ technology 1.5, treatment period with Control-IQ technology 2.0 at the standard target, and treatment period with Control-IQ technology 2.0 at the lower target, where the order of treatment periods will be randomized.

Primary Endpoints:

- Severe hypoglycemia (with cognitive impairment such that assistance of another individual is needed for treatment) during study compared with data on severe hypoglycemic events reported by T1D Exchange clinic registry over a 3-month time period

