3.3 Visit 6: Control-IQ 2.0 Training Visit

- After participants complete the run-in, they will return for the Control-IQ 2.0 training visit, and switch to
- the Control-IQ 2.0 study pump after training by qualified staff.
- Control-IQ 2.0 allow for selection of different glycemic targets, as well as toggling autoboluses in
- standard and exercise activity. The late bolus feature will also be available.
- Participants will be randomized to use either a daytime 30-min predictive glucose target of 90-130 mg/dL
- or 112.5 to 160 mg/dL for the first two-week period, then switch to the other target after 2 weeks.
- In the training visit, participants will:

327

328

329

332

337

345

346

347

348

349

350

351

352

353

354

355356

357

358

- 1) Select the appropriate target in clinic on their study pump per the randomization, and will be instructed by study staff to use the assigned glycemic target during each two week period.
 - 2) Be instructed that autoboluses will default to on during normal activity, and off during exercise activity.
 - 3) Be reminded again that use of the security PIN on the insulin pump will be required for anyone who is not entirely responsible for their own diabetes care, to include all 2-5 year olds, and those 6 years of age or older who may be only partially responsible for their own diabetes management.
 - 4) Be instructed that sleep activity will be required during Control-IQ 2.0 use. A sleep schedule should be programmed into the pump for use each night. Participants will be instructed to disable sleep or adjust the schedule on the nights of the late bolus meal challenges, then re-enable sleep activity as soon as the challenges are over, so it is used the rest of the night.
 - 5) Review prior training guidelines from the Control-IQ technology 1.5 training visit, and be taught how the new features are different in Control-IQ technology 2.0.
 - 6) Review the study meal late bolus challenges, to be performed twice in each two week period. Participants may also use late bolus as desired outside of the challenges.
- The participant will be given a User Guide as a reference as well as review the Hypoglycemia and
- Hyperglycemia Treatment Guidelines as part of the Study Participant Instruction Sheet. The study device
- training form will be completed.
- Participants will be instructed to download the study device prior to each phone contact or office visit.

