457 458	In addition, real-time CGM alerts will be sent to study staff providers (MD, DO, NP, PA) for all 2-5 year old participants throughout their use of Control-IQ 2.0 technology (all 4 weeks).

459	Chapter 4: Study Devices and Drugs
460	4.1 Study Devices
461	4.1.1 Insulin Pump
462 463 464	For the run in period, participants will use a study provided Tandem t:slim X2 with Control-IQ 1.5 technology (Investigational Device). For the treatment period, participants will use a study provided Tandem t:slim X2 with Control-IQ 2.0 technology (Investigational Device).
465	4.1.2 Continuous Glucose Monitoring
466 467	The study CGM is the commercial version of the Dexcom G6, which includes a transmitter and sensors. The CGM sensor will be replaced at least once every 10 days.
468	4.1.3 Blood Glucose Meter
469	The study blood glucose meter is the Contour® NEXT (Ascencia Diabetes Care).
470 471 472	Blood glucose levels will be measured using the study's blood glucose meter (glucometer) and the CGM device will be calibrated if needed using the study glucometer and strips in accordance with the manufacturer's labeling.
473	4.1.4 Ketone Meter
474 475	The study blood ketone meter is the Precision Xtra Blood Glucose and Ketone Monitoring System (Abbott Diabetes Care).
476 477	Blood ketone levels will be measured when needed to evaluate prolonged hyperglycemia. The blood glucose meter component of the Precision Xtra device will not be used.
478	4.2 Study Device and Drug Accountability Procedures
479 480	Device accountability and inventory will be documented to include detailed inventory records of the study CGM supplies, and Tandem insulin pump system.
481	4.3 Participant Access to Study Device at Study Closure
482 483 484	Participant will return all investigational study devices and supplies (insulin pump, CGM and related supplies) at study closure. Participant may keep the study ketone meter and study glucometer if these devices are not marked for investigational use only.

Chapter 5: Testing Procedures and Questionnaires

486	5.1 General Challenge Guidelines
487 488 489	All study participants will complete two late bolus meal challenges during each two week treatment period. Participants will be instructed to wait at least 48 hours after switching targets in the treatment period to perform the next set of challenges.
490	A minimum of 48 hours will occur between all challenges for each participant.

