516 517 518	 Full bolus for the given carbohydrates and calculated correction, given 45 minutes after starting the meal, based on calculated bolus dose using the bolus calculator (with full amount of carbohydrates entered).
519 520 521	• Full bolus for the given carbohydrates and calculated correction, given 45 minutes after starting the meal, based on calculated bolus dose using the bolus calculator (with full amount of carbohydrates entered) AND enabling the late bolus feature to 45 minutes later.
522	For each meal challenge, participants will:
523 524	1. Be in a fasting state for two hours prior to consuming the last meal of the day, with the last manual insulin bolus more than two hours prior to the meal.

- 525 2. For participants age 6+, only begin the meal challenge if CGM glucose is between 70 mg/dL and 200 mg/dL, and CGM trend arrow is not down.
- For participants age 2-5, only begin the meal challenge if CGM glucose is between 70 mg/dL and 250 mg/dL, and CGM trend arrow is not down.
- 529 Subjects with hyperglycemia > 200mg/dL will reschedule their challenge for another time. If < 530 To mg/dL, carbohydrate treatment can be given, after which the meal challenge can continue.
 - 3. Pediatric participants age 2-5 should have a meal with at least 20 grams of carbohydrates. Participants age 6-13 should have a meal with at least 35 grams of carbohydrates. All other participants should have at least 50 grams of carbohydrates for the study meal challenges. *Each participant should use the same meal for all of their meal challenges in the study. Participants will be encouraged to use the same frozen entrée of their choice for consistency.*
 - 4. Do their best to complete the meal within 30 minutes of starting to eat.
 - 5. Write down the start and end time of eating the meal, as well as the meal content (to include amount of carbohydrate, protein and fat) on the study provided logbook.
 - 6. Bolus for the meal 45 minutes after starting to eat, entering the full carbohydrate amount and using the recommended dose from the bolus calculator. For one of the two challenges during a single treatment period, use the bolus calculator but do not change the bolus time. For the other challenge during the same treatment period, use the bolus calculator but change the bolus time to 45 minutes late.

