2. CGM hypoglycemia outcomes, compared between the three study time periods 922 a. Overall % time <54 mg/dL 923 b. Overall % time <70 mg/dL 924 3. Times in ranges-overall (70-180 mg/dL, >180 mg/dL, >250 mg/dL, 70-140 mg/dL) compared 925 between the three study time periods 926 4. Mean glucose compared between the three study time periods. 927 5. Overall variability (CV and SD) compared between the three study time periods 928 6. Secondary endpoints 2 - 5 compared during daytime and nighttime, across the three study time 929 930 periods 7. Secondary endpoints 2 - 5 as well as adverse events, during the study meal challenge periods, for 931 late bolus feature use compared to normal bolus in the meal challenges. 932 8. Time to intervention for hypo- or hyperglycemia during the study meal challenge periods, for late 933 bolus feature use compared to normal bolus in the meal challenges. 934 935 9. Number of interventions for hypo- or hyperglycemia during the study meal challenge periods for late bolus feature use compared to normal bolus in the meal challenges. 936 10. Subgroup Analysis for all metrics by age cohort, baseline HbA1c cohort (HbA1c at baseline of > 937 7.5%, yes/no), and target activity use (standard target, lower target, sleep activity, exercise 938 939 activity). 940 8.5 Analysis Datasets 941 942 Safety analysis set: All participants who initiate the Treatment Period and use the study device at least one time (including training). 943 CGM analysis set: Any member of the Safety Analysis Set who has at least 24 hours of CGM data during 944 945 either Treatment Period. CGM data occurring within the meal challenge windows (from time of start of meal up to 5 hours afterwards [3 hours for age 2-5]) will not be used to determine whether a subject is 946 included in CGM analysis set or not. 947 948 Late bolus meal challenge set: Any member of the Safety Analysis Set who has at least 24 hours of CGM data during the Treatment Period, and who has at least 3 hours of CGM data for at least one meal 949 challenge. 950 8.6 Analysis of Endpoints 951 8.6.1 Analysis of the Safety Event Endpoints 952 953

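### The protocol does not say that the order of the normal-bolus and late-bolus meal challenges is randomised or counterbalanced, so secondary endpoints 7–9 can be confounded with challenge order

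*Combined protocol and SAP*

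**What the plan says.** **What is randomised.** Section 3.3 states: "Participants will be randomized to use either a daytime 30-min predictive glucose target of 90-130 mg/dL" or the other target first. The Study Endpoints part of the synopsis describes the three study periods in the same way, "where the order of treatment periods will be randomized". No other randomisation is described.

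**How the challenges are assigned.** Section 5.1.1 step 6 gives the normal-bolus challenge as "For one of the two challenges during a single treatment period, use the bolus calculator but do not change the bolus time", and the late-bolus challenge as "For the other challenge during the same treatment period, use the bolus calculator but change the bolus time to 45 minutes late". It does not say which is done first.

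**When they are done.** The footnote to the visit schedule spreads the challenges over each two-week period. Section 5.1 sets two spacing rules: "Participants will be instructed to wait at least 48 hours after switching targets", and "A minimum of 48 hours will occur between all challenges for each participant". Under Section 5.1.1 step 2, participants whose starting glucose is too high "will reschedule their challenge for another time".

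**What is compared.** Secondary endpoints 7, 8 and 9 (synopsis and Section 8.4) cover CGM outcomes and adverse events, time to intervention, and number of interventions. All three are for "late bolus feature use compared to normal bolus in the meal challenges".

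**How it is analysed.** Section 8.1 assumes no residual period or carryover effects for the crossover. Section 8.6.4 contains no term for challenge order.

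**The concern.** Target order is randomised, so a shift between the two treatment periods tends to average out of the target comparison. The late-bolus contrast is made within a period, between two evenings, and has no stated protection of that kind.

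Several things can differ between a participant's first and second challenge in a period:
- the second is further from the target switch;
- the same meal has been rehearsed once;
- staff have spoken with the participant after the first challenge (Section 5.1);
- the site may have adjusted pump settings (Section 3.7);
- the participant may have used late bolus in daily life, which Section 3.3 allows.

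The participant also knows which bolus is in use. Section 5.1.1 steps 7 and 8 allow an extra bolus or extra carbohydrate on symptoms, so experience or expectation can act directly on endpoints 8 and 9.

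At stake is whether a late-versus-normal difference can be read as the effect of the feature. Late-bolus challenges are part of the stated objective, and the balance cannot be restored once the challenges are done.

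**Working it through.** The plan gives no figure to reproduce for this contrast. Section 8.3 says that the sample size has no statistical basis, and no effect size, SD or order effect is stated.

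**Inputs from the documents.** Completers: 30 + 30 + 12 = 72. Challenges: 2 per period × 2 periods = 4 per participant, so 72 × 4 = 288 in all and 144 per bolus type. Testing: two-sided 5%, unadjusted (Section 8.16).

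**Inputs assumed.** p is the share of participants doing the late-bolus challenge second. δ is the effect of being second rather than first, in SDs of the paired difference. Both are shown over a range.

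**Bias in one period.** Let τ be the true feature effect. The expected late-minus-normal difference is τ + δ for a participant who does late second, and τ − δ for one who does late first. The mean is

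τ + pδ − (1 − p)δ = τ + (2p − 1)δ.

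The multiplier (2p − 1) is 0 at p = 0.5, 0.5 at p = 0.75 and 1 at p = 1.

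**False-positive rate.** Take a paired t-test on one period with τ = 0. The SD of the differences is s = √(1 + 4p(1 − p)δ²), and the noncentrality is (2p − 1)δ√n / s. For n = 72 and δ = 0.25:
- p = 1: 0.25 × 8.485 = 2.12, which gives 55.3%;
- p = 0.75: s = √(1 + 0.75 × 0.0625) = 1.023, then 0.125 × 8.485 / 1.023 = 1.04, which gives 17.6%.

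| n | δ (assumed) | p = 0.75 | p = 1 |
|---|---|---|---|
| 72 | 0.10 | 7.0% | 13.3% |
| 72 | 0.25 | 17.6% | 55.3% |
| 72 | 0.50 | 48.4% | 98.7% |
| 30 | 0.25 | 9.9% | 26.3% |
| 12 | 0.25 | 6.7% | 12.4% |

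At p = 0.5 the rate is 5% or slightly below, whatever δ is.

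**Self-selection.** If participants choose the order and happen to split evenly, the formula gives zero order bias. It does not cover a second route, in which bolus type is matched to the kind of day. That bias can remain at p = 0.5, and nothing in the documents allows it to be sized.

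**Effect of counterbalancing.** Let the order effect differ by period, δ₁ and δ₂. A participant with late second in period 1 and late first in period 2 has mean difference τ + (δ₁ − δ₂)/2. The reverse allocation gives τ − (δ₁ − δ₂)/2. With half of each, the average is τ, so the order effect need not be the same in both periods.

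**Why balance and not simple randomisation.** Under simple randomisation the SD of (2p − 1) in one period is 1/√n: 0.118 for 72, 0.183 for 30 and 0.289 for the 12 preschoolers.

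**The case against.** **The documents are silent; they do not describe an unbalanced order.** This stands. Section 5.1 refers to a logbook with instructions, reviewed with each participant, and requires staff contact before each challenge. The logbook is not available and could set an order. A reader might infer that the choice is left to the participant, but no section says so. A single fixed order in the logbook would make the confounding complete, so only a balanced rule answers the point.

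**The worst case has little textual support.** This also stands. A reader might infer that everyone does the normal bolus first, because both lists in Section 5.1.1 put it first. But the two components are unnumbered bullets and step 6 is neutral on order. Likewise, Section 3.7 allows setting changes at any time, and nothing places them between the two challenges.

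**The setting is already well controlled.** Partly stands. The same meal, a two-hour fast, dinner only, starting-glucose limits, restricted extra insulin and food, and the 48-hour gaps reduce day-to-day noise. They do not balance order.

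**The endpoints are exploratory.** This stands on severity. Section 8.2 sets no formal hypotheses, but exploratory status does not remove bias from an estimate.

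**There is no model to take an order term.** Correct. Section 8.6.4.1 averages the two challenges within a period, Section 8.6.4.2 compares the two targets, and Section 8.6.4.3 gives summary statistics by treatment period. The fix must therefore specify the late-versus-normal analysis first. Because both challenges enter the average, the averaged CGM comparison between targets does not depend on which bolus type came first.

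**Conclusion.** The concern holds in a limited form. The protocol does not state that challenge order is randomised or counterbalanced, and no planned analysis accounts for it, so the contrasts in endpoints 7–9 can be confounded with order. If the order is self-selected, they can also be confounded with choice of day.

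The size is (2p − 1) times an unknown order effect. The false-positive rates above show sensitivity over assumed values and predict nothing about this trial; the order effect may be negligible. The documents do not support saying that the contrast is confounded as a matter of fact, or that the whole order effect enters the estimate. The primary safety endpoints are untouched. The change should be made, but it does not decide whether the trial is sound.

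**What to change.** 1. At Visit 6, allocate challenge order together with the target sequence. Half the participants do normal then late in period 1, half late then normal, and each reverses in period 2. Crossed with target order this gives four allocation cells, to be balanced within age cohort: 12 preschoolers make 3 per cell, and 30 make 7 or 8.
2. Print the assigned order in each participant's logbook. State that a rescheduled challenge keeps its assigned bolus type and place in the order.
3. Record the actual order and date of every challenge in the eCRF.
4. Add to Section 8.6.4 a within-participant late-versus-normal analysis for each of endpoints 7–9, with challenge order as a term alongside bolus type, target and period. For time to intervention, the model should allow for repeated challenges in the same participant.

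**Cost.** This is a cheap improvement, though not a free one. It needs a small protocol and logbook amendment, with IRB approval before use (Section 10.2), a longer allocation list, and tracking of adherence to the assigned order when a challenge is rescheduled. It adds no visits or procedures, and changes no dose or safety rule.

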5.2 Laboratory Testing

5.2.1 HbA1c

531

532

533

534

535

536

537

538

539

540

541

542

543

544

545

546

547

548

549

550

553

554

555

557

561

HbA1c measurement will be performed locally at the Screening visit.

5.2.2 Urine Pregnancy

- Urine pregnancy testing performed locally at clinical site for females of child-bearing potential at the
- screening visit, at the start of study device use (for both device training visits), and anytime pregnancy is suspected.

5.2.3 Patient Reported Outcomes

The following patient reported outcomes/questionnaires and study specific outcomes will be assessed during the trial as per the study visit schedule.

564 **INSPIRE Survey**

- 565 The INSPIRE (Insulin Delivery Systems: Perceptions, Ideas, Reflections and Expectations) survey was
- developed to assess various aspects of a user's experience regarding automated insulin delivery for both
- patients and family members. The surveys include various topics important to patients with type 1
- diabetes and their family members based upon >200 hours of qualitative interviews and focus groups. The
- adult survey includes 31 items; the adolescent survey includes 28 items; and the parent survey includes 30
- items. Response options for all surveys include a 5-point Likert scale from strongly agree to strongly
- disagree, along with an N/A option.
- Administration time is approximately 5 minutes.
- 573 System Usability Scale (SUS)
- The System Usability Scale (SUS) is a 10-item questionnaire that measures the overall usability of a
- system. It is a valid and reliable measure of the perceived usability of a system and is technology-
- agnostic. The questionnaire presents statements with five response options (anchoring the options from
- strongly disagree to strongly agree) and asks users to rate their agreement to the statements. User scores
- are transformed into a composite score, from 0 to 100, and this score is taken as an overall measure of the
- system's usability; higher scores indicate better perceived usability.
- Administration time is approximately 5 minutes.
- 581 **Study Specific Questionnaire**
- A study-specific questionnaire will be used to assess experiences and views around the different target
- ranges, late bolus challenges, freedom to eat and adjust meals, and general thoughts about the trial.
- Administration time is approximately 5 minutes.

Chapter 6: Unanticipated Problem, Adverse Event, and Device Issue Reporting

6.1 Unanticipated Problems

- Site investigators will promptly report to the Coordinating Center and Sponsor on an eCRF all unanticipated problems meeting the criteria below. For this protocol, an unanticipated problem is an incident, experience, or outcome that meets all of the following criteria:
- Unexpected (in terms of nature, severity, or frequency) given (a) the research procedures that are described in the protocol related documents, such as the IRB-approved research protocol and informed consent document; and (b) the characteristics of the subject population being studied
- Related or possibly related to participation in the research (possibly related means there is a reasonable possibility that the incident, experience, or outcome may have been caused by the procedures involved in the research)
- Suggests that the research places participants or others at a greater risk of harm than was previously known or recognized (including physical, psychological, economic, or social harm)
- The Coordinating Center will report to the IRB all unanticipated problems not directly involving a specific site such as unanticipated problems that occur at another participating entity such as a pharmacy or laboratory. These instances must be reported to the study IRB within seven calendar days of
- recognition. The Sponsor will report to the appropriate regulatory authorities if the IRB determines that the event indeed meets the criteria of an Unanticipated Problem requiring additional reporting.
- the event indeed meets the criteria of an Onanticipated Problem requiring additional repo

